10. PHARMACODYNAMIC AND BIOMARKER ANALYSES

Biomarker Endpoints, Autoantibodies, complement, and peripheral B lymphocytes (referred to as B cells) will be collected per the study calendar (Section 15.2 Appendix 2: Schedule of Activities). The peripheral B lymphocytes will be measured (using FACS analysis). The specific biomarkers collected and analyzed are listed in Table 4:

Table 4 Biomarkers for Analysis

| Autoantibodies | Immunoglobulin |
|--|--|
| aCL (IgA, IgG, IgM) | IgG, IgM, and IgA |
| ANA | B cells (present in tables in this order) |
| Beta-2-glycoprotein (IgA, IgG, IgM) | CD19+ Total B cells (cells/mL) |
| Lupus anticoagulant | B cells CD20+ (cells/mL and % of CD19+ Total B cells) |
| Anti-dsDNA | Naive B cells IgD+ (cells/mL and % of CD19+ Total B cells) |
| | Naive CD20+ CD27- (cells/mL and % of CD19+ Total B cells) |
| Extractable nuclear antigens (ENAs) | Activated Total B cells CD95+ (cells/mL and % of CD19+ Total B cells) |
| Anti-Ribosomal-P ; | Memory CD20+ CD27+ (cells/mL and % of CD19+ Total B cells) |
| Anti-RNP-70; | Non-switched memory CD27+ IgD+ (cells/mL and % of CD19+ Total B cells) |
| Anti-SS-A; | Switched memory CD27+ IgD- (cells/mL and % of CD19+ Total B cells) |
| Anti-SS-B | Plasmablasts CD27b CD38b (cells/mL and % of CD19+ Total B cells) |
| Anti-Smith | Plasmablasts CD20+ CD27b CD38b (cells/mL and % of CD19+ Total B cells) |
| Complement | Plasmablasts CD20- CD27b CD38b (cells/mL and % of CD19+ Total B cells) |
| C3 | Transitional CD10+ CD24b CD27- CD38b (cells/mL and % of CD19+ Total B cells) |
| C4 | Transitional CD24b CD27- CD38b (cells/mL and % of CD19+ Total B cells) |
| T cells | Cytokines |
| CD3+ Total T cells (/uL) | BLyS (Total and Free) |
| CD8+ T cells (/uL) | |
| CD4+ T cells (/uL) | |

For the duration of the study, biomarker data (serum immunoglobulin isotypes IgA and IgM and B cell results) that have the potential to unblind the study team will not be transferred to the blinded study team. Instead, blinded datasets will only contain data from the baseline visit (hence not impacted by treatment group). These datasets will

display the format for the real datasets which will be received following unblinding. This will ensure that programs written using blinded data will still run on the real treatment codes and real unblinded data following the first database lock.

10.1. Biomarker Change and Percent Change from Baseline Analyses

| |
|---|
| Endpoints |
| The change from baseline and percent change (not for % endpoints) from baseline will be evaluated by visit for each of the biomarkers listed in Table 4 [T15.01-15.02, T15.04-T15.07, T15.09-T15.12, T15.14-T15.15, T25.01-25.02, T25.04-T25.07, T25.09-T25.12, T25.14-T25.15,]. Tables of descriptive statistics for changes in Year 2 relative to at the end of Year 1 will be summarised for immunoglobulins, auto-antibodies and B-Cells [T25.21, T25.22, T25.23]. |
| Population of Interest |
| The Intent-to-Treat population will be used for the analysis. |
| Intercurrent Event Strategy |
| The Year 1 analyses will be performed on the observed data up to IP discontinuation. No imputation will be done for missing data. The Year 1&2 analyses will be performed on the observed data for subjects who completed Week 52 on treatment (Ongoing and on treatment at Week 52 analysis as defined in Section 7.1.5). No imputation will be performed for missing data (data post re-start Belimumab will not be considered). |
| Model Specification |
| Immunoglobulins and Complement An ANCOVA will be used to evaluate the treatment effect controlling for treatment group, baseline SLEDAI-2K score (≤ 9 vs. ≥ 10), baseline immunosuppressant use (use vs. non-use), baseline corticosteroid dose (prednisone equivalent ≤ 10 mg/day vs. > 10 mg/day), and baseline value (continuous). If the distribution of the observed data is not consistent with conducting ANCOVA then a non-parametric rank ANCOVA will also be conducted. Auto-Antibody, B-Cells, T-Cells, and BLYS (Total and Free): A Rank ANCOVA will be used to evaluate the treatment effect controlling for treatment group, baseline SLEDAI-2K score (≤ 9 vs. ≥ 10), baseline immunosuppressant use (use vs. non-use), baseline corticosteroid dose (prednisone equivalent ≤ 10 mg/day vs. > 10 mg/day), and rank baseline value (continuous). |
| Model Checking & Diagnostics |
| For the ANCOVA analysis the Kolmogorov-Smirnov D statistic will be used to test the assumption of normality. Residuals will be reviewed to assess the homogeneity of variance assumption. |

Model Results Presentation

The tables will display:

- Baseline: the number subjects, number of subjects, mean, standard error, standard deviation, median, 25th percentile, 75th percentile, minimum, maximum for each arm
- the number of subjects, mean, standard error, standard deviation, median, 25th percentile, 75th percentile, minimum, and maximum, for each arm at each visit
- For ANCOVA analysed endpoints the LS Mean, standard error of the LS Mean, treatment difference for each arm, and 95% confidence interval (CI) for the comparison of Arm B vs Arm A; and Arm B vs Arm C will be presented at Weeks 52, 64, and 104
- For all endpoints the p-value for treatment difference for Arm B vs Arm A will be presented at Weeks 52, 64, and 104.

For change from baseline endpoints, a plot of LS means +/- SE or Median +/- Quartiles (dependent on observed data distribution) by visit and treatment group will be provided.

There will also be additional reporting of lab parameters (Haematology, chemistry, urinalysis and other chemistries) to explore the changes in Year 2 relative to at the end of Year 1. Descriptive statistic tables considering the change from Week 52 by visit for Year 2 will be produced [T25.16-25.19].

10.2. Shifts in Immunoglobulins, Autoantibodies, and Complement by Visit

| Endpoints [T15.03, T15.08, T15.13, T25.03, T25.08, T25.13]. | | |
|---|--|--|
| Shift tables will be used to summarize the changes in immunoglobulins, autoantibodies, and complement by treatment group and visit. Autoantibodies will be evaluated for shifts from positive to negative. Immunoglobulins and complement will be evaluated for shifts from Low to Normal/High. | | |
| Autoantibody | Positive | Negative |
| Anti-dsDNA | ≥30 IU/mL | <30 IU/mL |
| ANA | ≥80 Titer | <80 Titer |
| aCL | If any of the three aCL parameters, IgG (≥14 U/mL), IgA (≥11 U/mL) or IgM (≥12 U/mL), is positive. | If at least 1 is non-missing then aCL is negative; otherwise aCL is missing. |
| Beta-2-glycoprotein isotypes: IgA, IgG, IgM | ≥21 U/mL | <21 U/mL |
| Lupus anticoagulant | N/A | |
| ENAs | > Upper limit of normal range | ≤ Upper limit of normal range |
| Cytokines | | |
| BlyS (Total and Free) | <75 th percentile | ≥75 th percentile |
| Ig and Complement | Low | Normal/High |
| IgG | <6.94 g/L | ≥6.94 g/L |
| IgA | <0.81 g/L | ≥0.81 g/L |
| IgM | <0.48 g/L | ≥0.48 g/L |
| C3 | <90 mg/dL | ≥90 mg/dL |
| C4 | <10 mg/dL | ≥10 mg/dL |
| Statistical Analysis | | |
| Fisher's exact test will be performed within each baseline category to evaluate the treatment effect at Week 52 only. | | |
| Summary Measure | | |
| The difference in proportions Arm B (Combination)– Arm A (Control) will be used to measure the treatment effect. | | |
| Population of Interest | | |
| The Intent-to-Treat population will be used for the analysis. | | |

| Intercurrent Event Strategy |
|--|
| These analyses will be performed on the observed data up to IP discontinuation. No imputation will be done for missing data. |
| Variables |
| 
 Immunoglobulins, autoantibodies, and complement endpoints evaluated one at a time. |

| |
|--|
| 
 • Treatment (belimumab plus rituximab=1, belimumab plus placebo=0) |
| 
Results Presentation
 |
| 
For IgG, IgA, IgM, C3,C4, and C3 and C4 combined baseline data will be summarized as the number and percent of subjects who are low or normal/high at baseline. For post-baseline visits the data will be summarized by baseline status defined as low or normal/high. Among subjects low at baseline the shifts presented will be low to normal/high and low to low. Among subjects normal/high at baseline, the shifts presented will be normal/high to normal/high and normal/high to low.
 
For anti-dsDNA, ANA, aCL, Beta-2-glycoprotein, Lupus anticoagulant,ENAs and BlyS, baseline data will be summarized as the number and percent of subjects who are positive and negative at baseline. For post-baseline visits the data will be summarized by baseline status defined as positive or negative. Among subjects positive at baseline, the shifts presented will be positive to negative and positive to positive (no change). Among subjects negative at baseline, the shifts presented will be negative to negative (no change) and negative to positive.
 |
| 
Subgroup Analyses
 |
| 
Subgroup analyses will not be conducted
 |

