| SLEDAI-2K score (PI) [T11.26, T11.27 (MITT)]. | Continuous Categorical: <=9, 10-11, >=12 |
| PGA score [T11.26, T11.27 (MITT)]. | Continuous Categorical: 0-1, >1 – 2.5, >2.5 |
| SLICC/ACR Damage Index score [T11.26, T11.27 (MITT)]. | Continuous Categorical: 0, 1, >1 |
| SLE disease duration (years) [T11.26, T11.27 (MITT)]. | Continuous |
| SLEDAI-2K (PI) by organ domain and item at baseline [T11.29]. | Categorical: presented if Yes |
| Baseline immunoglobulin levels (g/L): IgA, IgG, and IgM [T11.30]. | Continuous value Categorical: - IgA: <LLN (0.81 g/L), >ULN (4.63 g/L) - IgG: <LLN (6.94 g/L), >ULN (16.18 g/L) - IgM: <LLN (0.48 g/L), >ULN (2.71 g/L) |
| Baseline levels of complement: C3 [mg/dL] [T11.26, T11.27 (MITT)]. | Continuous Categorical: high (>180 mg/dL), normal (90 - 180 mg/dL), low (<90 mg/dL) |
| Baseline levels of complement: C4 [mg/dL] [T11.26, T11.27 (MITT)]. | Continuous Categorical: high (>40 mg/dL), normal (10 - 40 mg/dL), low (<10 mg/dL) |
| Complement Level [T11.26, T11.27 (MITT)] | Categorical: At least one low C3/C4, No low C3/C4 |
| Anti-dsDNA [IU/mL] [T11.26, T11.27 (MITT)]. | Continuous Categorical: -positive (≥ 30 IU/mL) -negative (< 30 IU/mL) |
| Complement Level and anti-dsDNA Level [T11.26, T11.27 (MITT)]. | Categorical: At least one low C3/C4 and anti-dsDNA ≥ 30 IU/mL; Not (At least one low C3/C4 and anti-dsDNA ≥ 30 IU/mL) |
| Proteinuria (g/24h) [T11.26, T11.27 (MITT)] | Continuous value Categorical: <=0.5 >0.5-<1 1-<2 >=2 |

| PARAMETER | SUMMARY TYPE |
|--|--|
| Baseline autoantibody levels [T11.31]. | |
| ANA [Titer]. | Continuous Categorical: -positive (≥ 80 Titer) -negative (< 80 Titer) |
| anti-cardiolipin (aCL) | Continuous for each of aCL-IgA, aCL-IgG, aCL-IgM Categorical (Positive is ≥ 15) : -positive (if any of the three isotypes aCL-IgG, aCL-IgA or aCL-IgM are above the upper limit of normal) -negative (if at least one is non-missing and none of the isotypes above the limit of quantification) -missing (all three isotypes are missing) |
| anti-dsDNA and/or ANA positive | Categorical: Yes, No |
| Beta-2-glycoprotein [U/mL]. for each of the isotypes IgG, IgA, and IgM | Continuous Categorical: Positive (≥ 21 U/mL), Negative |
| Lupus anticoagulant | Continuous |
| RNA Interferon Signature [T21.16] | Continuous Categorical: Low, High |
| B cells and T-cells at Baseline [T11.32] | |

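### Three biomarker category rules in the SAP conflict: anticardiolipin has two sets of limits, the BLyS columns read in reverse, and lupus anticoagulant has no rule for its planned shifts

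*SAP*

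**What the plan says.** **Anticardiolipin.** SAP 6.3 defines the baseline category for T11.31 as "Categorical (Positive is ≥ 15", one number for all three isotypes and no unit. The text beside it reads "positive (if any of the three isotypes aCL-IgG, aCL-IgA or aCL-IgM are above the upper limit of normal" and "negative (if at least one is non-missing and none of the isotypes above the limit of quantification". A missing category applies only when all three isotypes are missing. SAP 10.2, which governs the shift tables, sets separate limits: "IgG (≥14 U/mL), IgA (≥11 U/mL) or IgM (≥12 U/mL), is positive". There, a participant who is not positive is negative if any isotype was measured.

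**BLyS.** The cut-off table in 10.2 opens with the column headings "Autoantibody | Positive | Negative". Further down, under a Cytokines sub-header whose column cells are empty, comes the row "BlyS (Total and Free) | <75 th percentile | ≥75 th percentile". The immunoglobulin and complement block below it has its own headings, Low and Normal/High. The presentation rules at the end of 10.2 put BLyS in the positive/negative list with the autoantibodies: "ENAs and BlyS, baseline data will be summarized as the number and percent of subjects who are positive and negative at baseline".

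**Lupus anticoagulant.** The same table in 10.2 marks it N/A and leaves the negative cell blank, and 6.3 summarises it as a continuous variable only. The presentation rules in 10.2 still name it among the markers to be shown as positive/negative counts and shifts.

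Section 10.2 attaches a Week 52 Fisher's exact test within each baseline category, and an Arm B minus Arm A difference in proportions, to these categories. Neither RAP addendum changes any of the three rules. The second addendum (2.1.13) keeps the autoantibody shift table (new 25.05) and the table of autoantibody change restricted to participants positive at baseline (new 25.04).

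**The concern.** These are derivation rules that a programmer must follow literally. For aCL, the same participant can be counted differently in two tables of one report, and the plan does not say which rule selects participants for table 25.04. For BLyS, the heading that means normalisation for every autoantibody in the list would cover participants whose BLyS rose. Direction matters here, because the protocol (Section 3.2) justifies continuing belimumab partly by its suppression of the BLyS rise seen after rituximab. For lupus anticoagulant, any row that appears would rest on an undocumented decision.

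**Working it through.** There is no stated figure to reproduce. The check compares the rules directly.

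**1. aCL: 6.3 against 10.2**

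| Isotype | T11.31 (6.3) | Shift tables (10.2) | Range where they differ |
|---|---|---|---|
| IgG | ≥15, no unit | ≥14 U/mL | 14 to <15 |
| IgA | ≥15, no unit | ≥11 U/mL | 11 to <15 |
| IgM | ≥15, no unit | ≥12 U/mL | 12 to <15 |

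This takes the 15 to be in the same unit as the 10.2 limits. Both rules call a participant positive if any isotype qualifies.

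- *Direction.* 14, 11 and 12 are all below 15, so everyone positive under 6.3 is positive under 10.2, and the reverse can fail. On a grid of whole values 0 to 30 for the three isotypes there are 31³ = 29,791 combinations. Neither rule is met in 14 × 11 × 12 = 1,848. The 6.3 rule is not met in 15³ = 3,375, so 3,375 − 1,848 = 1,527 are positive under 10.2 only. Both rules are met in 29,791 − 3,375 = 26,416, and none is positive under 6.3 alone. The grid shows direction, not how often real participants disagree.
- *Examples.* IgG 10, IgA 5, IgM 13 is not positive in T11.31 but positive in the shift table. So are IgG 14.5 with the other two at 5, and IgA 12 with the other two at 5. A participant with IgA 12 and IgG 20 is positive under both.
- *Gap inside 6.3.* Positive requires exceeding the upper limit of normal (or reaching 15), whereas negative requires that nothing exceeds the limit of quantification. A participant whose highest isotype lies between those two points is neither positive, negative nor missing. Section 10.2 has no such gap.

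**2. BLyS**

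- The only headings in force above the Cytokines row are Positive and Negative, and the presentation rules confirm that BLyS is reported that way. So <75th percentile = positive and ≥75th = negative.
- For the autoantibodies with a stated limit (anti-dsDNA, ANA, aCL, beta-2-glycoprotein, ENAs), positive is the high side.
- A rise across the cut-off therefore reads as positive to negative, and a fall as negative to positive.
- The source of the percentile is not stated. If it is taken from the study's own baseline values (pooled or by arm), about 0.75 × 280 = 210 of the target sample would be called positive and 0.25 × 280 = 70 negative; swapping the labels gives 70 and 210. This assumes that every participant has a baseline value. A percentile from an outside reference could give any split.
- Reversing the labels does not change the counts or the Fisher p-values. Each within-category 2×2 table is the same and appears under the wrong name.

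**3. Lupus anticoagulant**

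10.2 gives no cut-off and 6.3 gives no category, yet the 10.2 presentation rules require positive and negative counts. No participant can be classified from the text.

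**The case against.** The strongest reply is that this is less than it seems.

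- *The shift tables do not mislabel all three markers, as a reader might infer.* This stands. The aCL shift table uses one rule at baseline and at every visit and is internally consistent; its conflict is with T11.31. Lupus anticoagulant cannot be derived, which is not mislabelling.
- *The BLyS reversal rests on inherited headings.* The Cytokines cells are blank, and low-then-high matches the order of the immunoglobulin block, so a heading may have been omitted. That may explain the slip, but the presentation rules still ask for positive/negative BLyS shifts, and the only headings available give the reversed reading.
- *No BLyS shift output is separately listed.* This stands. The endpoint text of 10.2 names immunoglobulins, autoantibodies and complement, and the retained shift tables (25.02, 25.05, 25.08) are those three. The problem arises only where the BLyS shift presentation is implemented.
- *The BLyS rationale is tested elsewhere.* This also stands. The rank ANCOVA in 10.1, table 25.09 and the new biomarker figure 25.04 use continuous BLyS and keep its direction. The documents do not support an inference that the trial's BLyS conclusion would be reversed.
- *The 15 might be in another unit, or the upper-limit-of-normal wording might govern T11.31.* Neither can be excluded. Either would leave T11.31 without a stated unit or with two competing rules, so reconciliation is still needed.

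**Conclusion.** Wrong as written, and minor. For aCL, T11.31 and the shift table disagree in one direction only, and only for participants with no isotype at 15 or more and at least one in a range shown above; this assumes common units. It would overreach to say that every value in those ranges produces a disagreement, because another isotype can make the participant positive under both rules. The number affected cannot be obtained from the documents. A reader might also infer that the 10.2 limits are the right ones because they are isotype-specific and carry units; nothing in the documents shows which set is correct. For BLyS, the labels are reversed on the literal reading, with about 75% called positive if the percentile is internal to the study. For lupus anticoagulant, the shift row is undefined. The reach is exploratory biomarker displays and their Week 52 Fisher tests; no primary or major secondary endpoint depends on these categories.

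**What to change.** - **aCL:** settle on one set of limits, with units, confirmed against the assay's reference limits. Apply it in T11.31, the shift tables and table 25.04. Define positive as any isotype at or above its limit, negative as at least one isotype measured and none at or above its limit, and missing otherwise. Remove the reference to the limit of quantification from the category rule in 6.3.
- **BLyS:** label the columns Low (<75th percentile) and High (≥75th), report Low-to-High and High-to-Low shifts, and state the reference distribution for the percentile, separately for total and free BLyS.
- **Lupus anticoagulant:** give it a category rule, or delete it from the positive/negative list in 10.2.

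The cost is RAP wording and table labels, with no new data. The second addendum was written after the Week 52 analysis, so the sponsor should also check which rules were programmed for the Year 1 tables, rerun any that differ, and record that the aCL limits were chosen on laboratory grounds.

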11. PHARMACOKINETIC ANALYSES

11.1. Primary Pharmacokinetic Analyses

Descriptive statistics for serum belimumab (from all three treatment arms combined) and rituximab concentrations will be displayed for each visit for Year 1 and for Years 1&2 Combined. The tables will display the mean value, standard deviation, 95% confidence interval, geometric mean, geometric standard deviation, geometric 95% confidence interval, coefficient of variation (%), median, 25th and 75th percentiles, minimum, and maximum. No statistical tests will be performed [T16.01, T16.02, T26.01].

A line graph will be produced which displays the median belimumab or rituximab concentration values along with 25th and 75th percentiles by visit Year 1 and for Years 1&2 Combined [F16.01, F16.02, F26.01].

A listing of serum belimumab and rituximab PK concentration-time data will be presented [L16.01, L16.02, LL26.01].

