This is a Phase 3, multi-center, 3-arm, randomized, double-blind, placebo-controlled, 104 week superiority study to evaluate the efficacy and safety of belimumab administered in combination with a single cycle of rituximab to adult participants with SLE. Participants will be randomly assigned to 1 of 3 treatment arms; belimumab plus rituximab-placebo (Arm A, control), belimumab plus rituximab (Arm B, combination), or open-label belimumab plus standard therapy (Arm C, reference). Blinded independent assessors will conduct the SLEDAI-2K at key time points. An Independent Data Monitoring Committee (IDMC) will review the safety data on a regular basis.

Number of Participants:

A total of approximately 560 participants are expected to be screened, with a goal of randomizing at least 280 participants (50% screen failure rate).

The sample size may be increased up to a maximum of 320 participants if the dropout rate, missing data or number of major protocol deviations suggests further participants are necessary to ensure robust conclusions can be drawn. The decision to increase the sample size will be made without unblinding the trial.

Treatment Groups and Duration:

Overview

At least 280 participants will be randomized in a 1:2:1 ratio to 1 of 3 arms: belimumab plus rituximab-placebo (Arm A, control, target N=70), belimumab plus rituximab (Arm B, combination, target N=140), or belimumab plus standard therapy (Arm C, reference, target N=70). Arms A and B are double-blind; participants will receive belimumab 200 mg/week for 51 weeks. Arm C (reference) is an open-label arm with belimumab subcutaneous (SC) 200 mg/week and standard therapy for 104 weeks. Arm C (reference) will provide a qualitative reference to assess the relative performance of Arm A (control) and Arm B (combination) vs. currently available standard SLE therapy (Arm C). The concomitant medication rules and definitions of treatment failure are the same for the

double-blind control and combination arms, Arms A and B, but differ from those for the open-label reference arm, Arm C.

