Randomization and the first dose of belimumab should be completed within 35 days of initiation of screening procedures. Participants will be receiving stable standard therapy at entry. At randomization, participants will be stratified by their screening SLEDAI-2K score (≤9 vs. ≥10), by immunosuppressant use at screening (immunosuppressant use vs. no use) and by screening corticosteroid dose (prednisone equivalent ≤10 mg/day vs. >10 mg/day). Belimumab will be administered SC on Day 1 and then weekly (i.e., every 7 days ±1 day) through Week 51 for Arms A and B, and through Week 103 for Arm C. SC injections will be administered at alternating injection sites between the left or right thighs and the abdomen. Rituximab-placebo or rituximab will be administered by intravenous (IV) infusions at Weeks 4 and 6 for Arms A and B. Participants in Arms A and B will be administered a pre-medication regimen 30 minutes before each rituximab-placebo or rituximab infusion on Weeks 4 and 6, including methylprednisolone 100 mg IV or equivalent, an antihistamine, and acetaminophen or equivalent.

Participants in any arm who are deemed treatment failures for efficacy endpoints at any time during the study will be encouraged to remain in the study and continue to have all efficacy and safety assessments.

Participants randomized to Arms A or B who enter the study on immunosuppressants will discontinue immunosuppressants prior to or on the day of the Week 4 visit. Continuing the stable immunosuppressant dose until Week 4 allows participants to receive 3 weeks of belimumab SC prior to discontinuing their immunosuppressants. Corticosteroids may be adjusted as necessary during this transition period. If participants in Arms A and B receive immunosuppressants after the Week 4 visit they will be deemed treatment failures. Participants in Arm C will continue their stable immunosuppressants throughout the study at the discretion of the investigator. If participants in Arm C require an increased dose of their stable immunosuppressant after Week 12 or addition of a new immunosuppressant they will be considered a treatment failure.

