During the 52-week double-blind portion of the study, participants in Arms A and B who cannot tolerate discontinuation of immunosuppressants or taper of corticosteroids or, in the opinion of the investigator, require added therapy, will be considered treatment failures for the efficacy endpoints. Blinding to the treatment assignments in Arms A and B will be maintained. At the investigator's discretion, these participants may continue treatment with belimumab, and/or be treated with additional SLE therapies as necessary, including corticosteroids and/or immunosuppressants. Participants in Arm C who are unable to tolerate the corticosteroid taper or, in the opinion of the investigator, require increased doses of their baseline immunosuppressants or addition of a new immunosuppressant will be considered treatment failures for the efficacy endpoints.

Participants in Arms A and B will enter into the 52-week treatment-free, observational phase of the study after completing Week 52 (Weeks 53 through 104). "Treatment-free" refers to no active treatment with study treatment (i.e., belimumab and/or rituximab). Participants in Arm C will continue to receive belimumab SC and their stable immunosuppressants during Weeks 53 through 104. For participants in all three treatment arms, treatment with anti-malarials, NSAIDs, and/or corticosteroids with a prednisone equivalent dose of ≤5 mg/day will be allowed in Weeks 53 to 104.

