To assess pharmacokinetics of and biomarker response to belimumab and a single cycle of rituximab administered in a combination regimen to adult participants with SLE	 Belimumab and rituximab concentrations by visit Change from baseline in autoantibodies by visit Change from baseline in peripheral blood leukocytes including B cell subsets by visit Change in BLyS levels from baseline by visit
Exploratory: Patient Reported Work Productivity	
To explore the impact of belimumab and a single cycle of rituximab administered in a combination regimen to adult participants with SLE on patient experience and productivity	 Change from baseline in Work Productivity and Activity Impairment (WPAI): Lupus percent overall work productivity impairment score by visit Change from baseline in WPAI: Lupus percent activity impairment score by visit

STUDY DESIGN

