| Antiphospholipid antibodies (aCL, lupus anticoagulant, ± beta-2-glycoprotein-1) | | X | | | X | | | | X | | | | X | X | X | |
| Labs and Biomarkers | | | | | | | | | | | | | | | | |
| B cells subsets | | X | X | | | | X | | X | | X | | X | | X | X |
| BLyS Protein | | X | | | | | | | | | | | X | | X | |
| Immunogenicity: Belimumab | | X | X(f) | X(f) | X | | | | X | | | | X | X | X | X |
| Immunogenicity: Rituximab | | X | X(f) | X(f) | X | | | | X | | | | X | X | X | |
| Pharmacokinetics: Belimumab | | | X(f) | | X | | | | X | | | | X | X | X | X |
| Pharmacokinetics: Rituximab | | | X(g) | X(g) | X | | | | X | X(h) | | | | X | X | X |
| Genetic sample | | X | | | | | | | | | | | | | | |
| Exploratory Further Research | | | | | | | | | | | | | | | | |
| Blood Leukocyte Analysis (PBMC) (p) | | X | | | | | | | | | | | X | | X | |
| RNA for Interferon Signature | | X | | | | | | | | | | | | | | |
| B cell receptor (g) | | X | | | | | | | | | | | | X | X | |
| B cells subsets – (u) | | X | X | | | | | | | | | | X | | X | |
| Study Treatment | | | | | | | | | | | | | | | | |
| Training on use of Autoinjector | X | X | | | | | | | | | | | | | | |
| Dispense/Train or Collect Electronic Diary | | X | | | | | | | | | | | | | X | |
| Dispense Belimumab for weekly dosing (SC) | | X (i) | X (s) | | X | X | X | X | | X | X | X | | | | |
| Rituximab or Rituximab-Placebo (IV) | | | X (j) | X (j) | | | | | | | | | | X (j) | | |
| Discontinue immunosuppressants | | | X | | | | | | | | | | | | | |
| Initiate corticosteroid taper | | | | | | X (k) | | | | | | | | | | |

| Double-Blind Treatment Phase Procedures (D=Day, W=Week) | Screening (35 to 1 day(s) before D1) | Treatment Period – Arms A and B (a) | | | | | | | | | | | | Unscheduled Visit (l) | Early Withdrawal Visit (b) | Follow-up visit (8 weeks post last dose) |
|---|---|-------------------------------------|----|----|----|-----|-----|----------|-----|---------------|-----|----------|-----|-----------------------|----------------------------|--|
| | | D1 (Base-line) | W4 | W6 | W8 | W12 | W16 | W20, W24 | W26 | W28, W32, W36 | W40 | W44, W48 | W52 | | | |
| Target for steroid corticosteroid dose to reach prednisone equivalent ≤ 5 mg/day | | | | | | | | | X | | | | | | | |
| Study Visit Review Procedures | | | | | | | | | | | | | | | | |
| AE/SAE review | | X | X | X | X | X | X | X | X | X | X | X | X | X | X | X |

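### Belimumab concentrations are summarised with all three arms combined, so the Week 80 statistics describe no arm and no committed summary shows belimumab levels with versus without rituximab

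*SAP*

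**What the plan says.** RAP Section 11.1 begins its plan for the PK summaries with: "Descriptive statistics for serum belimumab (from all three treatment arms combined". The summaries are by visit, once for the first year and once for both years together, and no statistical tests are planned. The line graph in the same section (median and quartiles by visit) has no arm split either.

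The second RAP addendum returns to PK. Section 2.3.2 restricts the Year 1&2 analyses to participants who completed Week 52 on treatment. For Arms A and B it uses data only up to any re-start of belimumab in Year 2; for Arm C it uses data up to discontinuation of study drug. Section 2.1.16 keeps T26.01 with its modification column empty, Section 2.1.17 drops the end-of-study PK figures, and Section 2.1.18 keeps a listing of belimumab concentrations.

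Protocol Section 1 gives weekly belimumab "through Week 51 for Arms A and B, and through Week 103 for Arm C", and adds: "Participants in Arm C will continue to receive belimumab SC and their stable immunosuppressants during Weeks 53 through 104". The exploratory objective in Protocol Section 4 is "To assess pharmacokinetics of and biomarker response to belimumab and a single cycle of rituximab administered in a combination regimen". The endpoint attached to it is belimumab and rituximab concentrations by visit.

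**The concern.** A concentration summary is interpretable when the people in it are on the same regimen at the same time. In Year 2 they are not: Arms A and B are washing out while Arm C is at steady dosing. The addendum's own data rules treat these as different quantities, yet nothing tells the programmer to put them in separate columns. In Year 1 the belimumab regimen is common to all arms, but after Weeks 4 and 6 only Arm B has received rituximab. A pooled table therefore cannot show whether belimumab levels differ when rituximab is added, which is the natural question under a combination-regimen PK objective.

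At stake is the usefulness of one exploratory descriptive output, and the risk that a reader takes a pooled Week 80 value, or the shape of the two-year profile, at face value.

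**Working it through.** The plan gives no figure on this point to reproduce, so the check is of what the text would produce.

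**1. Scheduled belimumab PK samples** (RAP Section 15.2, Tables 5 to 8; same weeks in Protocol Section 2)

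| Visit | Arms A/B | Arm C |
|---|---|---|
| W4 (A/B before the first infusion), W8, W26, W52 | yes | yes |
| W60, W64, W72 | yes, off drug | no |
| W80 | yes, off drug | yes, on drug |
| W104 | no | yes, on drug |

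Week 80 is the only scheduled Year 2 visit where the arms mix. Early-withdrawal samples slotted to a planned visit under Section 15.3.1 could add a few more.

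**2. Time off drug at Week 80.** The Week 80 target is Day 561 (Section 15.3.1). The Week 51 dose falls on Day 1 + 51 × 7 = 358. The gap is 561 − 358 = 203 days, or 203/7 = 29 weeks.

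**3. Residual level in Arms A/B.** Assume single-exponential decline and no dose after Week 51. With half-life h, the remaining fraction of the on-drug level is r = 2^(−203/h). Half-life is an assumption, shown over a range:

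| h (days) | r |
|---|---|
| 14 | 0.004% |
| 21 | 0.12% |
| 28 | 0.66% |
| 42 | 3.5% |

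**4. Pooled Week 80 statistics.** At target allocation, Arms A/B are (70 + 140)/280 = 75% of the pool. With equal relative spread in each arm:

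- Pooled mean ÷ Arm C mean = 0.25 + 0.75r, which is 0.250 at h = 14 and 0.276 at h = 42.
- Pooled geometric mean, with the Arm C geometric mean set to 100, = 100 × r^0.75, which is 0.053 at h = 14 and 8.1 at h = 42.

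A simulated lognormal mixture, with an assumed between-subject CV of 30% to 70% in every arm and the Arm C median set to 100, gives:

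- pooled mean 26.1 to 33.7, against an Arm C mean of 104.4 to 122.1;
- pooled median 0.005 to 4.6;
- pooled CV 161% to 223%, against the 30% to 70% put in.

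The median reflects Arms A/B, the mean is pulled up by Arm C, and the CV mostly measures the gap between the two groups.

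**5. Shape across Year 2.** The pooled series falls from W60 to W72 (A/B only), is mixed at W80, and returns to the on-drug level at W104 (C only). That rise reflects a change in which arms contribute, not a change within participants.

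**6. Year 1 after the infusions.** At W8, W26 and W52, Arm B is 140/280 = 50% of the pool at target. If the geometric mean in B were a multiple g of that in A and C (set to 100), the pooled geometric mean would be 100 × g^0.5: 83.7 for g = 0.70, 89.4 for g = 0.80 and 111.8 for g = 1.25. Each is a single number with no comparator beside it, so g cannot be recovered from the table.

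**The case against.** The strongest reply is that the wording may only name where the data come from, with columns by arm set in the PK shells. Those shells (RAP Section 15.11.2) are not among the documents, and Section 11.1.1.1 points to PK reporting standards that the Appendix 5 text does not contain. Section 5.1 also defines three treatment descriptors for displays. A by-arm layout therefore cannot be excluded. But *combined* is the operative word, and the RAP says so where it intends arms to be separate: Section 8.3.8 for immunogenicity, and Sections 10.1 and 10.2 for biomarkers. Pooling remains the plain reading.

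Second, the protocol endpoint is concentrations by visit. No between-arm PK comparison is promised and no test is planned. That is right, and it is why this is a reporting improvement rather than a failure to deliver an endpoint.

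Third, all arms receive the same belimumab regimen in Year 1, and the Week 4 sample in Arms A/B precedes the first infusion, so pooling at Week 4 hides no rituximab effect. That also stands; the Year 1 point is confined to Weeks 8, 26 and 52.

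Fourth, a reader might infer that any rituximab effect on belimumab levels is lost. The documents do not support that. Subject-level concentrations are listed, and RAP Section 12.1 names the effect of rituximab on belimumab PK as an aim of a population PK analysis. That analysis is, however, optional and post hoc, so no summary is committed.

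**Conclusion.** The point holds at low severity. Followed as written, Section 11.1 gives Week 80 statistics that describe no arm, a Years 1&2 profile whose shape depends on which arms were sampled, and post-infusion Year 1 summaries that merge rituximab-exposed and unexposed participants.

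The exact Week 80 values rest on the assumed half-life, spread and 3:1 split. The conclusion does not: for any Arm C share strictly between 0 and 1, the pooled mean lies between an off-drug and an on-drug level.

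Two wider readings are not supported. One is that off-drug and on-drug participants are mixed throughout Year 2; scheduled mixing is at Week 80 only. The other is that 210 and 70 participants would contribute there. Those are randomisation targets, whereas T26.01 is limited to those who completed Week 52 on treatment, with the arm-specific cut-offs above, so the numbers will be smaller and the ratio may differ.

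The objective is exploratory, and nothing here touches the primary or major secondary analyses.

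**What to change.** Amend RAP Section 11.1 so that belimumab concentrations are presented by arm (A, B, C) at each visit in T16.01, F16.01 and T26.01 (T16.01 and F16.01 taken, from their order of mention, as the belimumab outputs). In T26.01, show Year 2 washout in Arms A and B separately from Arm C on treatment. F26.01 needs no change, because end-of-study PK figures were dropped. If the PK shells already have arm columns, removing the word *combined* from Section 11.1 is enough.

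The cost is three columns instead of one, with no new samples, tests or multiplicity adjustment. The second addendum was written after the Year 1 analyses, so changing T16.01 and F16.01 means re-running two completed outputs. If that is unwelcome, a by-arm T26.01 still covers the Year 1 visits for participants who completed Week 52 on treatment.
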